Patients will receive continued care surveillance whether they are on or off medication if their blood pressures remain (SBP ≤ 150 or DBP ≤ 100) and they are not having any concerning symptoms. If they are on treatment with antihypertensive medication at discharge from the hospital the goal is for patients to remain with normal to mild range blood pressures and they will require the medication be titrated upwards to achieve adequate control (SBP ≤ 140 -150 or DBP ≤ 90 -100) as needed. If severe hypertension develops after discharge, and the blood pressures are SBP ≥ 150 or DBP ≥ 100 and the patient is not on medication we will recommend initiating medication as an outpatient. Alternatively, the medication may need to be titrated downward or discontinued if indicated due to the patient development of hypotension (SBP ≤ 90 or DBP ≤ 60).

The mobile health nurse will be reviewing the incoming blood pressures daily. Options for the enrolled patients care management are to report the concerning vital signs to the

patients primary provider or the primary provider can agree to have the Perinatal Service providers manage the abnormal vital signs. All providers for the enrolled patients are contacted and informed of enrollment and then typically they plan for the patients to be followed and managed with the mobile health team and any concerning vitals are addressed by the Perinatal Service and then communicated regarding any management decisions by EPIC-electronic medical charting.

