Concerning vital signs are SBP ≥ 150 or DBP ≥ 100 or SBP ≤ 90 or DBP ≤ 60 , which is the same as prior to discharge from the hospital. After the program began using the above paragraph which outlines need for medication initiation or management – it was acknowledged patients were requiring the initiation and management of their vital signs or medications often, i.e. approximately 40-50% of the patients. Therefore, the mobile health nurses needed a written document with the standard practice to determine the thresholds patients would need to initiate or titrate medications up or down. Therefore we developed algorithms as proposed in this modification that would help manage this care. In addition, as needed the patient will be instructed to call their provider as needed for any concerning vital signs or symptoms if the nurses are not available or as needed. If the patient does not have any concerning symptoms the abnormal vital signs will be discussed with the patient by the patient's provider or the nurse. If the patient is asymptomatic then there is the ability to refer to the management algorithm and then initiate medication or increase/decrease the dose of the medication per the algorithm. The algorithm is based off the standard of care – it is just to ease the communication and care coordination of the patients. The mobile health nurse will notify a doctor with initiation of medication.

It is expected that the patients with gestational hypertension or preeclampsia diagnoses will be able to titrate off of the antihypertensive medication between 14 -42 days postpartum. The recommendation to discontinue the antihypertensive medication can be performed if the patient has (SBP ≤ 120 or DBP ≤ 80) by the 14-day follow-up visit. If they are unable to do so by the 42-day follow-up visit they will likely be diagnosed with chronic hypertension (persistent elevation of blood pressure SBP ≥ 140 or DBP ≥ 90 by 12 weeks postpartum. It is expected that patients with chronic hypertension may need to continue this therapy beyond the study endpoint of 42 days.

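### The continue, adequate-control and stop-medication rules join systolic and diastolic limits with *or*, so one controlled value is enough; the stop rule is met at 145/78 with no alert

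*Combined protocol and SAP*

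**What the plan says.** The rules are in section 6, under the follow-up procedures for patients.

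- **Continue surveillance**, on or off medication: "if their blood pressures remain (SBP ≤ 150 or DBP ≤ 100" and there are no concerning symptoms.
- **Adequate control**, the goal of upward titration: "achieve adequate control (SBP ≤ 140 -150 or DBP ≤ 90 -100) as needed".
- **Stop medication**, a step that may be recommended and is not required: "if the patient has (SBP ≤ 120 or DBP ≤ 80) by the 14-day follow-up visit".
- **Alert**: "Concerning vital signs are SBP ≥ 150 or DBP ≥ 100 or SBP ≤ 90 or DBP ≤ 60". The same section says that "any concerning vitals are addressed by the Perinatal Service", typically by agreement with the primary provider.
- **Reference level**: the sentence after the stop rule describes chronic hypertension as "persistent elevation of blood pressure SBP ≥ 140 or DBP ≥ 90 by 12 weeks postpartum".

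Section 6 adds that these instructions proved insufficient in use, since about 40-50% of patients needed medication started or managed. "Therefore we developed algorithms as proposed in this modification that would help manage this care". Those algorithms are not reproduced in the text under review.

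On severity, the treatment-start sentence reads "If severe hypertension develops after discharge, and the blood pressures are SBP ≥ 150 or DBP ≥ 100". The table in section 3.3 (preeclampsia with severe features) and the readmission paragraph of section 6 use 160/110. The hypotheses for Aims 2, 3 and 5 (section 2) name severe hypertension without citing a level or a qualifying reading. Controls for Aims 3 and 5 come from chart review.

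**The concern.** *Or* is correct when a rule flags abnormality, because one high value is enough to worry about. It is wrong when a rule declares control, because both values must be acceptable. The alert uses *or* correctly. The three in-control rules copy the same connective and so can be satisfied by one value alone.

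This matters most for the stop rule. It is a printed condition for withdrawing treatment, and some readings that meet it lie in the protocol's own hypertensive range without reaching the alert. The text also describes the intervention being evaluated and is meant to inform a later trial, so the error could be carried forward.

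The related outcome question affects Aims 3 and 5. If severe hypertension were counted from daily home readings in one group and from chart entries in the other, the monitored group would show more of it through extra measurement alone. That would work against the stated hypothesis of a lower incidence.

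**Working it through.** The plan gives no figure on this point, so there is none to reproduce. The check is one of logic.

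**Inputs** (section 6)
- Continue: SBP ≤ 150 or DBP ≤ 100
- Control: SBP ≤ 140-150 or DBP ≤ 90-100
- Stop: SBP ≤ 120 or DBP ≤ 80
- Alert: SBP ≥ 150 or DBP ≥ 100 or SBP ≤ 90 or DBP ≤ 60
- Reference level: SBP ≥ 140 or DBP ≥ 90

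**Single readings, rules as printed**

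| Reading | Continue | Control (upper end) | Stop | Alert | At or above 140 or 90 |
|---|---|---|---|---|---|
| 145/78 | met | met | met | no | yes |
| 118/94 | met | met | met | no | yes |
| 165/78 | met | met | met | yes | yes |
| 165/95 | met | met | not met | yes | yes |
| 145/112 | met | met | not met | yes | yes |

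The last three rows are contradictions, since one rule says carry on and another says escalate. The first two are the silent gap. With *and* in the stop rule, neither 145/78 nor 118/94 meets it.

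**Grid.** Take all integer pairs with SBP 70-220, DBP 40-140 and SBP > DBP. There are 151 × 101 = 15,251 pairs, less 71 + 70 + … + 1 = 2,556 with SBP ≤ DBP, leaving 12,695.

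*Stop rule met, at or above 140 or 90, no alert:*
- SBP 140-149 with DBP 61-80: 10 × 20 = 200.
- DBP 90-99 with SBP 91-120 and SBP > DBP: 30 + 29 + … + 21 = 255.
- Total 455, with no pair in both zones. With *and*, SBP ≤ 120 and DBP ≤ 80 exclude both zones, so the count is 0.
- In the second zone, each of the 10 diastolic values has 19 pairs with a pulse pressure below 20 mmHg. That is 190 of the 455, so 455 − 190 = 265 remain.

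*Continue rule met together with the high side of the alert:*
- Pairs below both 150 and 100: 80 × 60 − 465 = 4,335. High alert: 12,695 − 4,335 = 8,360.
- Pairs that fail the continue rule (SBP > 150 and DBP > 100): 70 × 40 = 2,800. Overlap with *or*: 8,360 − 2,800 = 5,560.
- With *and* and non-strict limits, only the boundary overlaps: 61 + 50 − 1 = 110.
- With *and* and strict limits (< 150 and < 100), the overlap is 0, and no pair is left under neither rule.

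*Strict continue rule met together with the low side of the alert:* 80 × 21 = 1,680 with DBP ≤ 60, plus 9 + 10 + … + 29 = 399 with SBP ≤ 90 and DBP above 60, giving 2,079. An example is 110/58. Changing the connective does not settle these, so the text also needs a sentence on precedence.

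**Severe hypertension across the protocol.** The treatment-start sentence attaches the word to 150/100; section 3.3 and the readmission paragraph use 160/110. Section 6 defines the daily home value as the mean of three readings, while section 3.3 asks for two occasions at least 4 hours apart. Neither is tied to the outcome in the aims, the analysis plan (section 7.2) or Appendix I. For controls after discharge, Appendix I lists emergency and triage visits by date and time (items 42-43), clinic follow-up appointments by date and time (items 95-100), readmission data, and a blood pressure at the 6-week visit (item 56). It lists no home readings.

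**The case against.** The stop rule is permissive and tied to a planned clinic evaluation at 14 days. A woman taken off medication stays under daily nurse review, and 150/100 is the level for starting treatment again. Clinicians may well read the rule as *and*. These points stand: they limit the harm, although none of them bars the stop itself at 145/78.

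The 140/90 level in the neighbouring sentence concerns a diagnosis by 12 weeks, not an action at day 14, and 145/78 lies within the upper end of the control range. That is fair. But 140/90 is also the entry criterion (section 3.2) and one of the two levels named in section 6 for starting medication before discharge. Whatever the action level, a stop limit of 120 was not plausibly meant to be met at 145.

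The grid is arbitrary, and many of its pairs are unusual readings. This also stands. The counts show where the rules overlap and say nothing about how often.

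A reader might infer that women with uncontrolled pressure were taken off treatment, or that readings such as 165/95 went unnoticed. The documents support neither. The alert covers 165/95, no treatment decisions are reported, and the nurse algorithms are not in the supplied text, so nothing can be concluded about what they say. A reader might also infer that the protocol has no severity level. It has one, 160/110, but the aims do not cite it. Nor would counting home readings flatter the intervention: that bias runs the other way. Aims 2-5 are exploratory and unpowered (section 7.1), which lowers the stakes without removing the bias.

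**Conclusion.** The point holds as a wording error in a stated decision rule. All three in-control rules are met when only one value is controlled. For the continue and control rules, this contradicts the alert at or above 150/100. For the stop rule, it leaves an uncovered zone: SBP 140-149 with DBP 61-80, and DBP 90-99 with SBP 91-120. No frequency can be given, because the documents contain no blood-pressure distribution.

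The conclusion rests on reading the printed text literally and on taking 140/90 as the protocol's hypertensive level. Accrual closed on June 11, 2018 with 214 enrolled, so for these women it is a matter of reporting what was done. For a future trial it is a rule to correct.

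The severe-hypertension point is smaller. The missing threshold is mainly missing detail. The unequal measurement between daily home readings and chart review is real, but it can be avoided by choosing sources available in both groups.

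**What to change.** **Care rules, section 6.**
- Continue surveillance, and call control adequate, when SBP < 150 and DBP < 100.
- Medication may be stopped when SBP ≤ 120 and DBP ≤ 80.
- State that the concerning-vital-sign rule takes precedence over all three.
- Check that the nurse algorithm matches, and report the rules actually applied to the enrolled women.

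The cost is a few words and one document check. The downside is small: *and* also delays stopping at readings such as 122/70, which the printed rule would allow.

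**Severe hypertension.** Remove the word from the 150/100 treatment-start sentence, and use SBP ≥ 160 or DBP ≥ 110 in Aims 2, 3 and 5. For the group comparison in Aims 3 and 5, do not count home readings. Limit it to items already collected in both groups: hypertension readmission, emergency and triage visits, and the 6-week blood pressure. Use home readings only to describe the monitored group. This needs no new chart extraction. Note in the report that monitoring may itself change who attends, so some difference in ascertainment can remain.

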7.1. Sample size calculation

Aim1:

Our sample size calculation is based on numerous assumptions.

To estimate rates of participation and retention a sample size of 50 subjects we will be able to estimate a participation rate of 80% to within a 95% confidence interval of $\pm 10\%$ and a retention rate of 60% to within a 95% confidence interval of $\pm 13\%$.^{13,14,15,16} Adjusting for up to a 10% drop out rate we increased the sample size to 55 subjects.

Aims 2-5; are not powered as they are exploratory outcomes that will be used for future study planning. However, there may be up to 440 subjects available to include in this analysis. This was determined knowing there are 30 mobile units available at all times. The endpoint is at 6 weeks. So, this would allow for 30 patients in the first month and then on a rolling basis approximately 20 patients could be recruited per month at max enrollment. This would total 220 patients using mobile health for the 1-year experimental period. The control group would be subjects matched within the same month of experimental subjects and be a 1:1 matching. So the control group would consist of up to 220 patients. The numbers may be less due to lower rates of recruitment/participation.

Aim 7-8:

The original study is closed to accrual, with a total of 214 subjects enrolled. With the success of the study, UPH-Meriter decided to incorporate the home monitoring program into its standard clinical services as of January 1, 2019. Through UPH-Meriter, 358 patients received services through this clinical program.

We would like to retrospectively review the patient data in Peridata for these 358 patients. We will collect home vital sign data to assess blood pressure trends from early pregnancy through pregnancy and postpartum. This additional data would help to increase our sample size in this evaluation. The same data would be collected from the clinical patients.

Therefore, our sample size would increase. We enrolled 214 subjects in the original Telehealth study, with 214 matched controls. 358 patients received remote monitoring services from the UPH-Meriter program. 100 providers with delivery privileges at UPH-Meriter were offered the opportunity to complete a survey regarding the research. The new sample size is 886 patients. We do have prior IRB approval to collect data from Peridata for our original study patients.

1. Non-compliance policies

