4.2. Screening for eligibility and consent

For aims 1-5

Inpatient

We will screen for subjects on a daily basis by reviewing the patients admitted to postpartum unit. Patients will be approached if the electronic medical record indicates a diagnosis of hypertension or the patient meets the blood pressure criteria for enrollment. This screening will be performed by the mobile health nurse providing support for this program or the research coordinator as needed. If a patient is identified, the patient's nurse or care provider will be contacted to ask the patient if they are interested in learning more about the study.

Outpatient

I have also met with the providers providing obstetrical care to patients (midwives and physicians who practice at UW Health- [name], UW Health- Fitchburg, UW Health- West, UW Health- West Towne, UW Health- Union Corners, Associated Physicians) who express interest in providing this experimental clinical program for their patients. Providers may discuss this project with their patients who have hypertension affecting their pregnancy. They will also have access to the patient brochure and can give this to the patients they believe meet criteria for the study. If they identify a patient who is interested in participating they will directly contact a member of the research team to further discuss enrollment with the patient. In addition, the floor nurses will know the inclusion criteria and may contact a member of the research team for recruitment, however this is not expected.

Finally, a patient can inquire and express interest in participating the program and contact the research coordinator directly with the phone number contact provided in the study flier. The patient inclusion and exclusion criteria will be verified as well as the participant's interest in the study. The informed consent process will be conducted by trained research staff and will include all aspects of the study and full disclosure of the risks, benefits, and alternatives. The study consent and HIPPA authorization form (see appendix) will be signed after all questions have been discussed and answered.

4.3. Data management:

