9.1 Dropout

A subject is considered to have “dropped out” of the study if they are randomized but later decide to discontinue participation. Because of the potential compliance issues in postpartum patients and possible side effects of the drugs, we anticipate a dropout of 10%. Participants will be asked in the consent form to allow follow-up via medical records after they drop out. Every effort will be made to ask subjects to complete a withdrawal form, which will allow us to learn more about why the subject chose to leave this study. As with crossover patients, all patients who drop out of the study will be included in the analysis on an intention to treat principle.

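### Aim 1 precision figures: 50 subjects give about ±11%, not ±10%, at 80% participation; the denominators and interval method are not stated, and the 10% drop-out allowance does nothing for the retention estimate

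*Combined protocol and SAP*

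**What the plan says.** Section 7.1 (Aim 1) opens with "To estimate rates of participation and retention a sample size of 50 subjects". For participation it claims a half-width of ten percentage points, in the clause "we will be able to estimate a participation rate of 80% to within a 95% confidence interval of". The matching claim for retention, thirteen percentage points, is in the clause "and a retention rate of 60% to within a 95% confidence interval of". The allowance for loss comes last: "Adjusting for up to a 10% drop out rate we increased the sample size to 55 subjects". No interval method is named, and neither rate is given a denominator.

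The Dropout section (numbered 9.1, within the non-compliance policies) repeats the allowance: "we anticipate a dropout of 10" percent. It describes drop-out as a subject's later decision to stop taking part and keeps such subjects in the analysis by intention to treat. The subject withdrawal policy at the end of Section 6 likewise analyses everyone enrolled.

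Section 7.2 makes willingness and 42-day retention the Aim 1 primary outcome, with attrition as a secondary outcome.

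Section 4.2 gives several routes into the study. Under daily screening, "the patient's nurse or care provider will be contacted to ask the patient if they are interested in learning more". Providers may refer, and "a patient can inquire and express interest in participating the program" directly.

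**The concern.** Three things do not fit together.

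- **Precision.** The ±10% is tied to 50 subjects, and 50 subjects do not give it.
- **Denominator.** The abstract, the endpoints paragraph and Section 8 all treat the 55 as enrolled women. In Section 8, the 14% of about 400 hypertensive patients a year is 55/400 = 13.75%. A participation rate needs the women who were offered the study, including those who said no. Section 7.1 does not identify them, and Appendix I lists no item for women approached or declining.
- **Loss.** A paragraph that assumes 60% retention then allows for 10% drop-out, without saying how the two differ.

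Aim 1 exists to supply rates for planning a later trial. That trial would inherit a willingness rate and a loss rate, so a reader must be able to tell what each is a proportion of, and whether the expected loss is nearer 10% or 40%.

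**Working it through.** **Inputs.** From Section 7.1: n = 50; participation 80%, ±10%; retention 60%, ±13%; drop-out 10%; final size 55. From the Dropout section: 10%.

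**Step 1: the stated half-widths.** Wald formula: 1.96 × √(p(1 − p)/n).

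- 80%, n = 50: 1.96 × √(0.16/50) = 11.1%
- 60%, n = 50: 1.96 × √(0.24/50) = 13.6%

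Other 95% intervals (half of total width):

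| | Wald | Wilson | Agresti-Coull | Jeffreys | Clopper-Pearson |
|---|---|---|---|---|---|
| 80%, n = 50 | 11.1% | 10.9% | 11.1% | 10.9% | 11.8% |
| 60%, n = 50 | 13.6% | 13.1% | 13.1% | 13.3% | 14.2% |
| 80%, n = 55 | 10.6% | 10.4% | 10.6% | 10.4% | 11.3% |
| 60%, n = 55 | 13.0% | 12.5% | 12.6% | 12.7% | 13.5% |

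At n = 50 no method gives ±10% for participation. For retention, three of the five round to ±13% and two do not. At n = 55 Wilson and Jeffreys round to both stated figures, but the text attaches the figures to 50, before the allowance is added.

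**Step 2: the n that Wald would need.**

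- ±10% at 80%: 1.96² × 0.16/0.10² = 61.5, so 62
- ±13% at 60%: 1.96² × 0.24/0.13² = 54.6, so 55

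**Step 3: participation on the women approached.** This assumes that everyone enrolled came through screening.

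- 50 enrolled at 80%: 50/0.80 = 62.5 approached; 1.96 × √(0.16/62.5) = 9.9%
- 55 enrolled at 80%: 55/0.80 = 68.75, about 69 approached; 1.96 × √(0.16/68.75) = 9.5%

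The stated ±10% is therefore recovered from 50 enrolled women once the denominator is the women approached.

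**Step 4: the drop-out step.** 50 × 1.10 = 55 reproduces the final size (50/0.90 = 55.6, so 56, by the usual formula). Retention of 60% means 100% − 60% = 40% not retained, against 10% drop-out. For the retention rate itself, a woman who leaves before day 42 is a known non-retained subject. She counts in the denominator and not in the numerator. Nothing is lost from n, so there is nothing for the allowance to restore.

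**The case against.** The strongest defence is that the plan's numbers work once read sensibly. With the women approached as denominator, 50 enrolled give ±9.9% and 55 give ±9.5%. With all 55 enrolled as denominator, retention at 60% is ±13.0% by Wald. Both targets are met without recruiting anyone further. This stands, and it limits the point to one of statement and definition. A reader might infer that Aim 1 is undersized or that its precision is not delivered; the documents do not support that.

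A reader might also call the ±13% an error. It is not one outright, because Wilson, Agresti-Coull and Jeffreys all round to 13% at n = 50 and the plan does not commit to Wald.

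A reader might take 10% drop-out against 60% retention as a flat contradiction, and conclude that the sample should be inflated for 40% loss (50/0.60 = 83.3, so 84) or that too few completers would remain. The text does not go that far. Drop-out is described as an active decision to stop, attrition is listed separately from retention, and Section 13.2 distinguishes drop-out from failure to send daily readings. Formal withdrawal of 10% could coexist with 60% completing 42 days. What stands is that no passage says so. Inflation is not needed on either reading, since retention is estimated over everyone enrolled.

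Finally, it is tempting to say that participation cannot be computed, or that self-referral biases it upward. Daily screening could supply the denominator, and the documents give no count of self-referrals from which to size a bias.

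The study is closed to accrual with 214 monitored subjects. If retention were reported on all of them, the half-width at 60% would be 1.96 × √(0.24/214) = 6.6%, so the choice between 50 and 55 would matter little.

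**Conclusion.** The point holds as a minor correction. The ±10% does not follow from 50 subjects under any of the five 95% intervals tried; the shortfall is 0.9 to 1.8 percentage points. It follows from 50 enrolled only with about 62 women approached as the denominator, which is not stated. The ±13% lies between 13.1% and 14.2% at n = 50, depending on the method. The 50-to-55 step serves no purpose for retention, and the relation between 10% drop-out and 60% retention is undefined.

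The conclusion rests on reading the 50 and 55 as enrolled women, as the rest of the protocol does, and on keeping drop-outs in the analysis, as the protocol provides. It does not show that the sample is too small.

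**What to change.** Restate Section 7.1 for Aim 1:

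- **Participation** = women who consented / eligible women identified by screening and offered the study, counting those who decline when first asked by the nurse or provider. Show self-referred women separately. At 80%, 55 enrolled implies about 69 approached and about ±9.5%.
- **Retention** = women retained to day 42 / all 55 enrolled, about ±13% at 60%.
- Name the interval method and use it for both rates.
- Delete the 10% inflation and give 55 directly as the size.
- Reconcile the 10% in the Dropout section with the 60% retention, or define drop-out there as formal withdrawal, distinct from not completing 42 days.
- If women who declined were not logged, state that participation is not estimable and report retention only.

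The cost is a few sentences in Sections 7.1 and 9.1 (Dropout) and a count from the screening records, if they exist. The sample size does not change and no further patients are needed.
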